#### **4.2 Rationale for Study Design**

Several design features are employed in the current study in an effort to minimize bias, including a double-blind design, with patients randomly assigned to NasoVax or placebo on a 1:1 basis. Random assignment of patients avoids bias and helps ensure that both known and unknown risk factors are distributed evenly between treatment groups. The use of placebo control permits prospective comparison between the active treatment group and the control group.

In order to mitigate the risk of exposure to SARS-CoV-2 at the study center and reduce the use of personal protective equipment, all data after administration of study drug will be collected remotely, either electronically or via telephone; no in-person visits post-vaccination are required unless a participant experiences a change in symptoms or AE that requires a visit for assessment. After study drug administration on Day 1, patients will be evaluated remotely.

The study design adheres to the March 2020 FDA Guidance on the conduct of clinical trials during the COVID-19 pandemic (Centers for Disease Control and Prevention, Coronavirus Disease 2019 (COVID-19): Groups at Higher Risk for Severe Illness, Updated May 14,

---

2020 <https://www.cdc.gov/coronavirus/2019-ncov/need-extra-precautions/groups-at-higher-risk.html#serious-heart-conditions> (last accessed June 7, 2020)

United States Food and Drug Administration (2020).

To ensure further the safety of participating patients, a DMC will review safety data after each cohort is enrolled and throughout the study. If any safety concerns are identified, the DMC will make a determination regarding continuation of the study; the DMC may be unblinded for this review. The DMC will oversee all aspects of the study to optimize the safety of study participants. Stopping Rules have also been developed for the further protection of patients.

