## **6.5 Blinding and Unblinding**

The Pharmacy staff will be unblinded for the purpose of final drug preparation. The pharmacist will consult the unblinded study statistician for dose allocation and the Pharmacy staff will prepare each dose in compliance with the randomization list.

---

Due to the fact that formulations cannot be made to look identical, a blinded syringe will be used for administration. Study staff either preparing the syringes and/or administering the study drug will be independent and will not take part in any other activity of the study (eg, telephone contact).

Knowledge of the randomization list will be limited to the persons responsible for creation of the randomization list, pharmacy staff who prepare the study drugs, and any unblinded study monitors or auditors, until all data collection and verification activities and assignment of patients to the analysis populations has been completed, the database has been locked, and the study formally unblinded.

Data provided to the DMC may be unblinded, as required, for the assessment of safety.

If unblinding is required in the interest of the safety of a patient, an Investigator will discuss the matter with the Sponsor before unblinding. In a medical emergency, the Investigator or delegate may unblind via the IWRS for that patient without prior consultation with the Sponsor. In that event, the Investigator or delegate will notify the Sponsor as soon as possible that the randomization code has been broken for the patient. If the blind is broken, the date, time, and reason must be recorded.

Patients may also be unblinded for the assessment of Stopping Rules, DMC evaluations, expedited safety reports, and the emergency unblinding of individual patients, as detailed in a separate Safety Management Plan.

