9.5 Analysis Populations

Consented Population: All patients who signed the informed consent.

Randomized Population: All patients who were randomized to receive any study medication.

Safety Analysis Set: All patients who receive any study drug. Patients will be analyzed according to the treatment that they receive.

Modified Intent-to-Treat (mITT) Analysis Set: All randomized patients who receive any amount of study drug, have a Baseline and at least one post-Baseline resting SpO₂ measurement. Patients will be analyzed according to the treatment that they receive. Patients will be analyzed according to the treatment that they receive. This analysis set will be used for primary and secondary analyses.

Per Protocol (PP) Set: All randomized patients who receive any amount of study drug according to the correct treatment assignment and who have 80% of twice daily results from resting SpO₂ measurements through Day 14 or hospitalization.

All important protocol deviations documented during study will be collected and finally assessed as major or minor protocol deviation after data base lock and prior to unblinding.

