9.6 Summary of Study Data

For all summaries described in the SAP, the patients enrolled in the ALT-601-201 and randomized to an active dose will be summarized/listed under the heading "NasoVAX", while patients enrolled in Placebo will be summarized/listed under the heading "Placebo".

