9.9 Analysis of Efficacy Data

Efficacy analyses will be conducted using the mITT and PP Populations with the primary conclusions drawn from the mITT Population. Placebo will be the collective (pooled) across cohorts.

Descriptive statistics will be used to evaluate differences between Baseline and post-Baseline efficacy endpoints. The study is considered exploratory, and inferential statistics will be employed as appropriate.

For the purpose of study efficacy endpoints, resting SpO₂ and resting pulse rate will be assessed on observed data only; if data is missing, it will not be imputed.

The p-values from significance tests will be obtained at a one-sided significance level of 0.025.

No multiplicity adjustments will be made for the efficacy endpoints.

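### The mITT set behind the primary efficacy conclusion is grouped by treatment received, while SAP 9.6 labels summaries by randomized arm; a misdosed patient has no settled arm

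*SAP*

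**What the plan says.** **Grouping rule for the efficacy set.** SAP 9.5 defines mITT as randomized patients who received any study drug and have a Baseline and at least one later resting SpO2 value. It then states: "Patients will be analyzed according to the treatment that they receive. This analysis set will be used for primary and secondary analyses". Protocol 10.2 carries the same wording. In both places the as-treated sentence appears twice in a row. The protocol synopsis has it once under mITT and gives no grouping rule for the Safety set.

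**Role of the set.** SAP 9.9 runs efficacy on mITT and PP, "with the primary conclusions drawn from the mITT Population".

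**Labelling rule.** SAP 9.6 covers all summaries in the SAP. It says that patients "randomized to an active dose will be summarized/listed under the heading" NasoVAX, and that those enrolled in placebo go under Placebo.

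**Other sets.** SAP 9.5 also defines a "Randomized Population: All patients who were randomized to receive any study medication", but no efficacy analysis is assigned to it. PP takes "All randomized patients who receive any amount of study drug according to the correct treatment assignment", subject also to 80% of the twice-daily SpO2 results.

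**Purpose of randomizing.** Protocol 4.2 says: "Random assignment of patients avoids bias and helps ensure that both known and unknown risk factors are distributed evenly between treatment groups".

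**The concern.** Treatment received is the usual grouping for safety. For efficacy, the comparison protected by randomization is between the arms as assigned. If a patient given the wrong syringe is moved to the other arm, the groups compared are no longer those that randomization formed, and the balance claimed in Protocol 4.2 is no longer assured for that patient.

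The SAP also disagrees with itself. A patient randomized to NasoVAX who received placebo counts as placebo under 9.5 and appears under NasoVAX under 9.6. Neither document says which section governs. SAP 9.13 settles only conflicts between the SAP and the protocol, and Protocol 10.4, which holds the primary analysis fixed, refers back to a protocol with the same as-treated rule.

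At stake is the pre-specification of the primary comparison. If a misdose came to light after unblinding, someone would have to choose that patient's arm knowing the result. With about 48 patients per arm and a one-sided test at 0.025, a single patient can matter.

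**Working it through.** The plan states no power, effect size or event rate, so it has no figure to reproduce on this point. The planned size is consistent: 20 + 28 + 48 = 96 patients, and 10 + 14 + 24 = 48 per arm. All event counts below are assumptions.

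**Step 1. Where one misdosed patient falls**

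| Rule | Randomized to NasoVAX, given placebo | Randomized to placebo, given NasoVAX |
|---|---|---|
| SAP 9.5 and Protocol 10.2, mITT | placebo | NasoVAX |
| SAP 9.6, table heading | NasoVAX | placebo (reading enrolled in placebo as randomized to it) |
| SAP 9.5, PP | excluded | excluded |

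No row keeps the patient in an efficacy analysis under the randomized arm.

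**Step 2. Effect on the difference**

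Assume 5/48 NasoVAX and 10/48 placebo events as randomized. The difference, placebo minus NasoVAX, is 20.83% − 10.42% = 10.4 points. Moving one patient to the arm received gives four cases.

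| Misdosed patient | NasoVAX | Placebo | Difference |
|---|---|---|---|
| Assigned NasoVAX, got placebo, worsened | 4/47 = 8.51% | 11/49 = 22.45% | 13.9 points |
| Assigned placebo, got NasoVAX, did not worsen | 5/49 = 10.20% | 10/47 = 21.28% | 11.1 points |
| Assigned NasoVAX, got placebo, did not worsen | 5/47 = 10.64% | 10/49 = 20.41% | 9.8 points |
| Assigned placebo, got NasoVAX, worsened | 6/49 = 12.24% | 9/47 = 19.15% | 6.9 points |

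The range is 6.9 to 13.9 points. Only 15 of the 96 assumed patients have an event, so a misdosed patient would more often be a non-event, and the shift would be about 0.6 points.

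**Step 3. Effect on the test**

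The test used here is the unstratified Mantel-Haenszel test, one-sided. Let a be NasoVAX events, n1 and n0 the NasoVAX and placebo arm sizes, m total events and N = 96. Then z = (a − n1·m/N) / √V, with V = n1·n0·m·(N − m) / (N²·(N − 1)). The planned test is stratified, so these p-values are indicative only.

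- **5/48 vs 10/48:** z = (5 − 7.5)/√3.197 = −1.40, p = 0.081. In the first case above, 4/47 vs 11/49, z = (4 − 7.344)/√3.196 = −1.87, p = 0.031. The threshold is not crossed.
- **4/48 vs 10/48:** z = (4 − 7)/√3.021 = −1.73, p = 0.042. If one NasoVAX-assigned patient with an event received placebo, the table is 3/47 vs 11/49: z = (3 − 6.854)/√3.020 = −2.22, p = 0.013. The one-sided Fisher p moves from 0.073 to 0.0245. Both tests cross 0.025.
- **The opposite direction, 3/48 vs 10/48:** z = (3 − 6.5)/√2.840 = −2.08, p = 0.019. If one placebo-assigned patient with an event received NasoVAX, the table is 4/49 vs 9/47: z = (4 − 6.635)/√2.838 = −1.56, p = 0.059. Significance is lost.

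**Step 4. Errors unrelated to prognosis**

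As-treated grouping then has no expected bias. As-randomized grouping dilutes the effect. With k patients per arm swapped, the expected difference is (p0 − p1)(1 − 2k/48), where p0 and p1 are the placebo and NasoVAX risks. With assumed risks of 20% and 10% and k = 1, this is 10.0 × (1 − 2/48) = 9.6 points.

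**The case against.** **The rule may never operate.** Study personnel give one dose on one occasion (Protocol 6.9), and the pharmacy prepares it from the randomization list (Protocol 6.5). No error rate is given. The study is exploratory and was not sized for significance. This stands, and it lowers the severity.

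**A reader might infer that the as-treated rule breaks the randomized comparison or favours NasoVAX.** The documents do not support that. Nothing changes without a misdose, errors unrelated to prognosis give no expected bias, and a single error can move the estimate either way.

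**A reader might infer that no efficacy analysis is as randomized.** That goes too far. Every PP patient was correctly dosed and so is in the randomized arm. The gap is narrower: no efficacy set retains misdosed patients in the arm to which they were assigned.

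**A reader might infer that dosing errors are likely, or that the rule was copied from the Safety set by accident.** Patients are registered through the IWRS, and for dosing "The pharmacist will consult the unblinded study statistician for dose allocation", but nothing says that these are separate allocation sources. The pharmacy manual is a separate document. The doubled sentence suggests a drafting slip, yet the synopsis has the rule once, under mITT only, which fits a deliberate choice equally well.

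**SAP 9.6 may be only a heading convention.** Its placebo half says enrolled rather than randomized, and the population definition in 9.5 could be read as controlling. That is a fair reading, but the text does not state it, and 9.6 claims all summaries.

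**A misdose would be visible.** Deviations from the assigned dose are handled as protocol deviations (Protocol 9.5), and SAP 9.7 lists the randomization allocation. An as-randomized result could be recomputed, but that does not pre-specify the primary one.

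**Conclusion.** The point holds as a defect of definition and consistency. The primary efficacy set is grouped by treatment received, SAP 9.6 labels by randomized arm, and misdosed patients have no as-randomized efficacy analysis.

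The effect is nil if no misdose occurs. Under the assumed 5/48 vs 10/48, one misdosed patient gives a difference between 6.9 and 13.9 points instead of 10.4. Under other assumed counts, one patient moves the one-sided p-value across 0.025 in either direction. These figures rest on assumed events, the full 48 per arm in mITT, and an unstratified test. They show sensitivity and do not predict bias.

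Severity is below must-fix, because misdosing should be rare and the study is exploratory. The point still merits correction, because the change is small and has to precede unblinding to be credible.

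**What to change.** Before unblinding:

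1. **mITT.** In SAP 9.5, Protocol 10.2 and the synopsis, state that mITT patients are analysed by the treatment to which they were randomized. Delete the duplicate sentence in 9.5 and 10.2.
2. **Safety set.** Keep treatment received in SAP 9.5 and Protocol 10.2, and add that rule to the synopsis, whose Safety definition has none.
3. **SAP 9.6.** Limit the as-randomized headings to efficacy tables. Head Safety-set tables by treatment received, including the disposition tables that SAP 9.7 bases on the Safety Population. Putting disposition under as-randomized headings would create a new conflict.
4. **Misdosed patients.** List them with assigned and received treatment. If there are any, add an as-treated sensitivity analysis of the primary endpoint.

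The cost is a small wording amendment to both documents, with written IRB approval for the protocol change (Protocol 12.5). No extra patients or data collection are needed. The statistical price, paid only if misdosing occurs, is slight dilution: 10.0 to 9.6 points in the example with one patient per arm swapped.

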3 STUDY ENDPOINTS

3.1 Primary Efficacy Endpoint

The primary endpoint is the proportion of patients with clinical worsening, defined as a 4.0% decrease from Baseline in resting SpO₂ by mobile pulse oximetry on two consecutive measurements during home follow-up, or hospitalization.

Baseline is defined as data collected closest to randomization prior to any study drug dosing. For resting SpO₂ and resting pulse rate, Baseline is defined as the average of the two measurements at Screening.

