After discharge on Day 1, patients will return home for the duration of the study. Patients are to measure resting SpO₂, resting pulse rate, and oral temperature twice daily at 09:00 hours and 16:00 hours, with a 1-hour window around each time point, and at any time they experience worsening symptoms until Day 14 or hospitalization, whichever comes first. Patients are to record COVID-19-related symptoms daily during this same time period. Study center personnel will contact patients daily by telephone during this period to document the patient's clinical status, record concomitant medications and monitor for AEs.

After Day 14, study center personnel will contact patients via telephone approximately every 7±2 days for 14 additional days to determine if they were hospitalized and to follow AEs that were not resolved by Day 14. If the patient is hospitalized at any time, the dates and times of hospital admission/discharge, ICU admission/discharge, and ventilation requirement are to be recorded, as applicable. Patients who remain hospitalized at the end of 28 days will be followed through Day 42 or death, whichever is sooner.

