4.2 Schedule of Events

The schedule for study activities is presented in [Table 2](#).

Confidential

Table 2 Schedule of Events – Screening and Treatment Periods

Procedure	Study Visit Type / Day			
	Screening	Study Drug Treatment	Diary Completion/ Telephone Contact	Telephone Contact
	Study Center Visit		Remote Visit	
	Day 1 Pre-Dose	Day 1	Daily Days 1 to 14	Days 21 and 28 ±2 days
Informed consent	X			
Eligibility criteria check	X			
Demographics	X			
Medical history	X			
Focused cardiovascular and respiratory physical examination	X			
Height and weight	X			
Blood pressure and respiratory rate	X			
Urine pregnancy test ^a	X			
Randomization	X			
Study drug administration ^b		X		
Resting SpO ₂ ^c	X		X ^d	
Resting pulse rate ^c	X		X ^d	
Oral temperature ^c	X		X ^d	
Baseline/Concomitant medications	X		X	X
AEs			X	X
eDiary completion for COVID-19 symptoms ^e	X		X	
Criteria for the Assessment of Severity of Illness in Patients with COVID-19 ^f	X			X
Daily telephone contact to document concomitant medications, clinical and hospitalization status and AEs ^g			X	
Follow-up contact for hospitalization status, COVID-19 outcomes, and AEs ^h				X

^a For women of child-bearing potential only. Results must be available and confirmed to be negative before study drug administration.

^b Study drug is to be administered with the patient in the supine position. The patient is to remain in the supine position for 30 minutes thereafter and be observed for at least 2 hours post intranasal administration.

^c To be measured remotely daily at 09:00 and 16:00 hours or at any time the patient experiences worsening symptoms using the study-supplied devices and recorded in the eDiary. Resting SpO₂ and pulse are to be measured at rest for 2 minutes. A ±1 hour window will be allowed. On Day 1, only the afternoon (16:00 hours) measurement is required and may be measured at the study center or remotely.

^d If the Screening visit occurs in the morning, the patient will be responsible for recording the 16:00 measurements at home later that day; if the visit occurs after 16:00, measurements will commence at home the following morning.

Confidential

- ^e The following symptoms will be recorded: fatigue, chills, headache, cough (with or without sputum production), myalgia, sore throat, shortness of breath, nasal congestion, diarrhea, and nausea or vomiting.

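### The Per Protocol completeness window closes at hospitalization but not at a home SpO2 event or a death outside hospital, so membership of the supportive set can depend on outcome

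*SAP*

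**What the plan says.** SAP 9.5, protocol 10.2 and the protocol synopsis share one PP rule. Patients must have been dosed "according to the correct treatment assignment and who have 80% of twice daily results from resting" SpO2 "measurements through Day 14 or hospitalization". No other end to the counting window is given.

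The primary endpoint (SAP 3.1) is a 4.0% fall in resting SpO2 "on two consecutive measurements during home follow-up, or hospitalization". It therefore has two components, one observed at home and one defined by admission. Death is not a named component. All-cause mortality through Day 42 is a separate secondary efficacy endpoint (SAP 3.2).

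Home readings are taken "twice daily at 09:00 hours and 16:00 hours, with a 1-hour window around each time point", and also "at any time they experience worsening symptoms until Day 14 or hospitalization, whichever comes first" (SAP 4.1). A home SpO2 event does not end measurement. For the first day, the footnotes to the schedule (SAP 4.2) say "On Day 1, only the afternoon (16:00 hours) measurement is required" and "if the visit occurs after 16:00, measurements will commence at home the following morning".

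On the role of the set, SAP 9.9 states: "Efficacy analyses will be conducted using the mITT and PP Populations with the primary conclusions drawn from the mITT Population". The mITT set needs only one post-Baseline reading.

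**The concern.** Two patients can both have a fully observed primary outcome and be treated differently. The one who worsens and is admitted is judged on readings up to admission. The one who worsens at home and then stops measuring is judged against the full 14 days and may be excluded.

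Stopping after worsening is foreseeable. Protocol section 8 provides for patients who cannot complete the diary or calls, and 7.1 allows withdrawal at any time. Section 8.2.1.2 requires room-air readings, while 6.7 records supplemental oxygen as a concomitant medication. The documents do not say how often any of this is expected.

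At stake is the value of the PP analysis. It is the only efficacy set besides mITT, SAP 9.1 calls for results in each set separately, and the sensitivity analyses in SAP 9.9.5 and 9.9.6 are optional. If membership depends on what follows an event, agreement or disagreement between PP and mITT is hard to interpret.

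**Working it through.** **No stated figure to reproduce.** The documents give no count of required readings, no event rate and no compliance rate. The planned size agrees: 2 × (10 + 14 + 24) = 96, or 48 per arm.

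**Readings required** (schedule from SAP 4.1 and 4.2; 80% read as at least 80%; symptom-triggered readings not counted):
- Day 1 afternoon plus Days 2–14: 1 + 13 × 2 = 27. Needed: 0.80 × 27 = 21.6, so 22.
- Visit after 16:00: 13 × 2 = 26. Needed: 0.80 × 26 = 20.8, so 21.
- Either way at most 5 may be missed.

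**Earliest day the rule can be met.** Readings by the end of Day d are 2d − 1 (or 2d − 2 after a late visit). By the end of Day 11 that is 21 (or 20). The requirement is first met at 09:00 on Day 12. With a nominal denominator of 28, 23 are needed, reached at 16:00 on Day 12.

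**Perfect compliance, then no readings and no admission** (denominator 27):
- end of Day 5: 9/27 = 33%, out
- end of Day 7: 13/27 = 48%, out
- end of Day 11: 21/27 = 78%, out

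A patient admitted at the end of Day 5 scores 9/9 and stays.

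**Continuing after a home event.** With full compliance before the event, the patient stays in PP by making 22 − 9 = 13 of the remaining 18 readings after Day 5, 22 − 13 = 9 of 14 after Day 7, or 22 − 19 = 3 of 8 after Day 10.

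**Illustrated effect on PP rates.** All rates are assumed. Let p be the true worsening rate, h the part that is hospitalization, s = p − h the part that is home SpO2 events, and q the share of home-event patients who stop and are excluded. If every other patient complies, the PP rate is [h + s(1 − q)] / [h + s(1 − q) + 1 − p]. With p = 20% on placebo and 10% on NasoVAX (true difference 10 points):

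| Events that are home SpO2 events | q | Placebo | NasoVAX | Difference (points) |
|---|---|---|---|---|
| all | 25% | 15.8% | 7.7% | 8.1 |
| all | 50% | 11.1% | 5.3% | 5.8 |
| all | 100% | 0% | 0% | 0 |
| half | 50% | 15.8% | 7.7% | 8.1 |

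With no true effect (20% in both arms, all home events), q = 25% on placebo and 50% on NasoVAX gives 15.8% vs 11.1%, a spurious difference.

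**The case against.** A reader might infer that the rule demands readings after any primary event, or that every patient with a known worsening is dropped. Neither is so. The window closes at admission, and a patient with a home event is asked to go on measuring and leaves PP only by missing more than 5 readings in total. The affected patient must stop measuring for days yet never be admitted, despite daily calls that ask about the need for a clinic or hospital visit (protocol Appendix A). This limits how many are affected; it does not remove the asymmetry.

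A reader might also infer that PP always understates the treatment effect. That depends on the scale. Suppose 12/48 vs 6/48 have events, 60% of them home SpO2 events, and half of those patients stop: 12 × 0.6 × 0.5 = 3.6 and 6 × 0.6 × 0.5 = 1.8 are removed. The rates become 8.4/44.4 = 18.9% and 4.2/46.2 = 9.1%, so the difference falls from 12.5 to 9.8 points. But the odds ratio is (6/42)/(12/36) = 0.429 before and (4.2/42)/(8.4/36) = 0.429 after, and the risk ratio moves from 0.50 to 0.48. Nor must the rates fall: if 30% of event-free placebo patients also miss the threshold, the placebo rate is 8.4/(8.4 + 25.2) = 25.0%, the true value, and above 30% it is too high. No direction can be claimed.

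A death outside hospital might be read as a lost primary event. Without an earlier SpO2 event or admission it is not one under the written definition. It is lost from the PP analysis of mortality, which is a secondary efficacy endpoint.

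Finally, PP is supportive, the study is exploratory, and SAP 9.7 tabulates the sets and lists exclusions, so removals would be visible. All of this stands and limits the importance of the point.

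**Conclusion.** The point holds as a gap in the definition of a supportive set. Two groups are excluded because of what follows an outcome: patients with a known home SpO2 event who miss more than 5 of the 27 or 26 scheduled readings in total without admission, and never-admitted patients who die before about the morning of Day 12. PP membership is therefore outcome-dependent.

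The counts follow from the schedule, given the readings of 80% and of unscheduled measurements stated above. The shifts in PP rates rest on assumed event rates and stopping shares; neither their size nor their direction can be determined from the documents. The defect does not extend to the mITT analysis, which has no 80% rule and carries the primary conclusion.

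**What to change.** In SAP 9.5, protocol 10.2 and the synopsis, require at least 80% of scheduled twice-daily readings up to the earliest of Day 14, first qualifying SpO2-based event (dated at the second of the two readings), hospitalization or death. State that the full schedule is 27 readings, or 26 after a late visit. Under this rule the patient with every reading up to an event at the end of Day 5 scores 9/9 and stays.

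Apply the same 80% test to every patient up to his or her own cut-off. Do not retain every patient with an event regardless of completeness, since that selects on outcome in the other direction. In the 12/48 vs 6/48 example, if 10% of event-free patients fail the test, keeping all events gives 12/(12 + 32.4) = 27.0% vs 6/(6 + 37.8) = 13.7%, a difference of 13.3 points instead of 12.5.

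The cost is one sentence in each place, before unblinding, with no change to data collection or the primary analysis. The small downside is that some patients with short follow-up enter the PP analyses of average SpO2 and pulse rate, as hospitalized patients already do.
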